## A. SIGNIFICANCE

**Prevalence.** Child maltreatment (CM) is a major public health problem in the US, affecting many lives, in the short-and long-term, and costing individuals, families and our society dearly. In 2015, 7.2 million children were reported to Child Protective Services (CPS). Of these, 683,000 children (i.e., 9.2 per 1000) were “substantiated” victims of child abuse and neglect. Yet, reported cases capture only the tip of the iceberg. The National Incidence Study (NIS-4), using observations by community professionals, estimated that 1.26 million children (i.e., 17.1 per 1,000) were maltreated in 2005-06, and the more inclusive “Endangerment Standard” estimated nearly 3 million victims (i.e., 40 per 1,000). **Outcomes.** The consequences of CM can be devastating - in the short- and long-term. In addition to injuries and physical health problems, child and adolescent sequelae include many psychological and behavioral problems. CM has also been linked to an array of adult outcomes such as substance use disorders, HIV/AIDS-related sexual risk behaviors and being a victim and/or perpetrator of intimate partner violence (IPV). Other problems in adulthood include depression, suicide, criminal behavior, interpersonal problems, and academic and vocational difficulties, as well as multiple physical health problems. **Costs.** The financial costs of CM are immense. The costs associated with injuries due to physical abuse far exceed the per-child costs of non-inflicted injuries of comparable severity. Two-thirds of the medical costs of CM are paid through Medicaid. Additional costs are incurred by the child welfare, educational, mental health, and judicial systems, with estimated U.S. costs of \$103.8 billion per year. The human and economic costs of CM point to the serious need for effective preventive strategies, and the broad implementation of evidence-based practices (EBPs).

**Need for and Potential of Primary Prevention of CM.** Despite the compelling need to prevent CM, few interventions other than home visiting programs (e.g., SafeCare) have been rigorously evaluated and found to be effective. Further, programs have not been developed for the healthcare system with the exception of preventing abusive head trauma, an important but small component of CM. The Safe Environment for Every Kid (SEEK) model, developed for pediatric primary care, was found to have helped prevent CM in two large federally f-funded, randomized controlled trials(RCTs), and is the focus of this proposal. Despite its success, as is often true with effective interventions, questions remain as to how best implement this model. The overall aims of the proposed study are to examine technology-driven approaches to implementing the model and to understand facilitators and barriers regarding its implementation and short-term sustainment, while also examining the effectiveness of these strategies. Doing so will advance knowledge in implementation science related to primary care and the prevention of CM.

The prevention of CM requires strengthening families, and supporting parents and parenting, thus fostering safe, stable, nurturing relationships (SSNRs). SSNRs in turn are important for promoting children’s health, development, and safety, and, for preventing CM. Ordway et al pointed out the critical role that healthcare professionals can play in promoting healthy relationships, stating “this requires a shift in pediatric healthcare’s focus to include families and communities, as well as a shift to include children’s social and emotional health.” Effective interventions in this area can achieve much more than preventing CM. Olds and colleagues, for example, found that the Nurse Family Partnership program led to fewer perinatal complications, more constructive modes of discipline, increased spacing of pregnancies, fewer problems with the justice system, and less use of illicit drugs and tobacco, in addition to reduced CM. Margolis et al found that interventions in pediatric practices resulted in fewer childhood injuries, less maternal smoking, and more stimulating home environments. In the 2nd SEEK RCT, mothers in the SEEK practices reported after 12 months fewer physical assaults by their partners than did controls (13% vs. 18%, p=.045). This helped explain the relationship between SEEK and fewer physical assaults of children by their mothers (1R49CE000588). Thus, the prevention of CM involves health promotion – for the child and family.

**Linking CM Prevention and Pediatric Primary Care.** The delivery of pediatric care by primary care providers (PCPs; i.e., pediatric and family medicine physicians, nurse practitioners and physician assistants) is via regularly scheduled checkups. As outlined by the AAP, “the foundation of Bright Futures health supervision is health promotion – not just preventing or treating illness or injury but actively promoting the physical, emotional, mental, and social well-being of children, adolescents, and their families.” Pediatric primary care is well positioned to play a valuable role: 1) it is well institutionalized, 2) prevention is a priority, 3) PCPs usually enjoy trusting relationships with families, 4) there are 12 visits from 0 – 5 years, 5) there is a longstanding concern with children’s safety, 6) PCPs often are the only professionals having contact with families of preschoolers, and 7) there is a broad commitment to children’s overall health, development and safety. Haggerty et al., in “The New Morbidity,” drew attention to major psychosocial problems, such as divorce, substance abuse and CM, jeopardizing children’s health and wellbeing. Bright Futures translated these ideas into practice guidance, urging consideration of a child’s environment. Parents also are interested in PCPs playing this broader role. Pediatric primary care’s potential was shown by Olson et al. where 40% of mothers who screened positive for depression accepted referrals for evaluation. Despite this, there only have

been modest shifts in practice. Sharpe et al. found that although psychosocial concerns were raised in 88% of checkups, pediatricians intervened in only 40%, partly due to feeling incompetent. The SEEK model was developed to fill this critical gap and take advantage of the excellent opportunity in primary care to help PCPs address common psychosocial problems known to be risk-factors for CM. Given the parameters of busy practice settings, the need for a low-burden, yet effective intervention was clear. Working with an Advisory Committee of neighborhood health center physicians, we factored in the time constraints and other screening efforts while developing SEEK. The two SEEK RCTs demonstrated the model's feasibility, with over 100 PCPs delivering the SEEK intervention. Moreover, although limited in reach compared to the vast number of primary care practices in the U.S., over 100 practices have indeed successfully adopted the model demonstrating real-world feasibility.

**Importance of Family Medicine.** While most children receive primary care in pediatric offices, about 1/3 receive this care by family physicians. More than 2/3 of family physicians provide pediatric primary care. Family medicine provides an excellent opportunity for implementing SEEK. Psychosocial problems top every list of common issues addressed. Family medicine PCPs usually care for the whole family, and are thus particularly well positioned to assess and understand how psychosocial risk factors can affect an entire family. These PCPs already encounter the problems by SEEK, and need to be equipped to address them.

[figure not shown]
**Implementation Science (IS) in Pediatric Primary Care Research.** The field of implementation science has recently experienced an “explosion” in the quality and quantity of research. Yet, a review of the Cochrane Effective Practice and Organization of Care (EPOC; <http://epoc.cochrane.org/our-reviews>) website under Implementation Strategies revealed no systematic reviews regarding primary prevention in pediatric care and none on screening related to CM. The proposed research will therefore contribute to implementation science in critical areas. Proctor, [name] and colleagues introduced the distinction between “intervention strategies” and “implementation strategies,” and the concept of “implementation outcomes” distinct from “service outcomes” and “client outcomes.” The current study aims are guided by this frame, including training and mode of delivery as implementation strategies, and examining implementation outcomes (e.g., adoption, feasibility, fidelity, penetration, acceptability, short-term sustainment, and costs), as well as SEEK’s effectiveness in preventing CM. The study will also contribute to the IS understanding of sustainment of innovations in service systems (e.g., pediatric primary care), an important yet little understood area in IS.

Common barriers to implementing and sustaining new interventions like SEEK include costs, time constraints, PCP attitudes, and failure to anticipate barriers to widespread implementation. The logistics in gathering PCPs for in-person training are formidable. Thus, many EBPs for primary care “die on the vine,” ripe fruit that is never picked. Webinars and online training, however, offer convenience and appear promising. However, even when implemented, effective strategies for sustaining EBPs in primary care are often lacking and thus discontinued due to factors such as poor integration into the work flow and lack of reimbursement.

To our knowledge, no other study has reported on implementation costs associated with a CM preventive intervention. To assess the costs of SEEK, we will measure the related costs and practice-level variations. To broadly disseminate effective interventions, practice costs and barriers to implementation and sustainment must be addressed. This is done by training and facilitating use of the intervention for adoption and integration into routine practice. The use of technology to facilitate accessibility, reliability, and fidelity of model components is an implementation strategy that increasingly fits with the workflow in primary care practices. It also helps integrate services into existing administrative activities (e.g., billing). Knowing the opportunity cost afforded by an intervention such as SEEK can overcome barriers related to PCP reluctance to adopt a new intervention, even if an EBP, without knowing the impact on practice resources. Thus, quantifying the implementation cost of SEEK is needed.

### The Safe Environment for Every Kid (SEEK) Model (see Figure 1)

Figure 1. Conceptual Model for SEEK

**Scientific Basis.** Two theories guided SEEK's development. Ecological-developmental theory recognizes the multiple and interacting systems surrounding a child. Pediatric care has focused narrowly on the child; SEEK was based on understanding the strong influence of family and parental functioning on children's health, development and safety, and on CM. SEEK was also guided by the Transtheoretical model

that links an understanding of a person's stage of change (e.g., pre-contemplative) with an intervention tailored to the individual. Principles of Motivational Interviewing (MI) too have been incorporated. Prevention science, Prevention science, integrating multiple disciplines, also guided SEEK's development. CM, with its multifactorial etiology, demands collaboration among disciplines. SEEK aims to effect such changes by enhancing PCPs' abilities to address the targeted problems, working with professionals in other disciplines and agencies. The SEEK model also has been guided by social cognitive theory. For example, role plays demonstrate how PCPs can address problems. Implementing these approaches, interacting with parents and behavioral health professionals and gaining confidence foster self-efficacy. In addition, the US Preventive Services Task Force recommends screening for intimate partner violence (IPV), depression, and alcohol misuse. SEEK provides a structured approach to follow this recommendation, and help prevent CM.

**The SEEK Model.** Core components include: 1) *training PCPs* to identify and help address targeted psychosocial problems that are prevalent risk factors for CM: parental depression and major stress, substance abuse, IPV, harsh discipline and food insecurity; 2) the evidence-based *SEEK Parent Questionnaire* (PQ) to screen for the problems at well child visits (see Appendix); 3) the Reflect-Empathize-Assess-Plan (REAP) approach to help PCPs assess and address problems; 4) principles of Motivational Interviewing; 5) *SEEK Parent Handouts* for each targeted problem, customized with local resources; and 6) a method for referring to community resources for identified problems –by the PCP or clinic team and office staff. Regarding the last component, SEEK practices in the RCTs had access to a social worker, although often problems were addressed by PCPs and office staff. A similar situation will apply in the proposed study where 60% of practices have behavioral health. In others, this will be done by PCPs and office staff. We think the "who" is not as important as the "what. This illustrates retaining core components while using strategies for scale-up in the "real world."

**Facilitation of Implementation of SEEK to be Examined in the Proposed Study.** The SEEK intervention has demonstrated effectiveness, but its widespread adoption by primary care clinics has been

limited. To help facilitate its implementation, two pragmatic technology driven platforms have been developed to increase the convenience and accessibility of the model to busy PCPs: 1) an interactive web-based training that utilizes webinars and individualized guidance during service delivery start-up and (2) a *SEEKonline* software to facilitate delivery of SEEK within regular primary care checkup

visits. This study will examine the effectiveness of these implementation strategies.

**Training.** Two training strategies will be tested (see Table 1), both increasingly used with PCPs, and developed in accordance with principles of adult learning. First, *SEEK Maintenance of Certification (MOC-4)* is an example of a structured Quality Improvement (QI) project approved by the American Boards of Pediatrics and of Family Medicine, required of physicians to maintain Board certification. It includes viewing the training videos and implementing SEEK in one's practice and conducting the QI Plan-Do-Study-Act cycle. This PDSA cycle involves learning from data collected before and during SEEK's implementation to assess and improve the process. Four one-hour webinars over 4 months enable collaborative learning and mentoring. Second, Independent online (IND) training is a student-centered approach; it involves viewing the training videos over 2-3 hours and passing the post-test. Both approaches include three 1-hour consultations in the ensuing year and offer CME credits toward state licensure. Although both are convenient, we hypothesize that the interactive MOC-4 training will lead to more efficient and competent adoption of SEEK.

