**Table 1. SEEK Training Strategies**

SEEK MOC-4	Independent Online (IND)
Eligible for MOC 4 and CME credits	Eligible for MOC CME credits
Engage in SEEK QI project – PDSA cycle	N/A
Participate in four 1-hr. webinars	N/A
View SEEK training videos (2.5 hours)	View SEEK training videos
Pass SEEK Post-test	Pass SEEK Post-test
Participate in 3 one-hour consultation sessions	Participate in 3 one-hour consultation sessions

**Facilitation of Service Delivery.** SEEKonline is software to efficiently implement SEEK via a secure web-based system interfacing with a practice's EHR. SEEKonline has been developed and is currently being beta tested. Its effectiveness in improving implementation outcomes compared to the Traditional paper-and-pencil approach has yet to be examined. Data are stored in a Microsoft SQL Server Database, in an isolated, secure, private cloud environment, behind a fully HIPAA-certified network security device. SEEKonline enables parents to privately complete the SEEK PQ before a child's checkup. Responses are available to PCPs

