### **Timeline** (See Table 3 for timing of data collection)

Month 1-8: Hire and train project coordinator and research assistant. Randomly select first 2 healthcare systems (one pediatric, one family medicine). Recruit practices and randomly assign to SEEK training strategies; complete training. Practices select SEEKonline or Traditional strategy, SEEKonline connected to practices' EHRs, computerize study protocol, obtain IRB approvals

Month 5-48: Periodic webinars with PCPs and evaluation of participants, develop papers and presentations

Month 9: Begin implementing SEEK model in cohort 1 of healthcare systems and practices

Month 11-15: Repeat above process with cohort 2 of healthcare systems and practices

Month 16: Begin implementing SEEK model in cohort 2

Month 46-48: End of observation period, practices decide whether to continue using SEEK, final surveys

Month 49-60: Data will be obtained from practices' EHRs re. implementation (e.g., rate of screening, CM-related ICD-10 codes), final data analyses, prepare Final Report and papers

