### **Procedures**

**Pre-implementation Phase** (5 months). Recruitment will begin and we will identify a physician "champion" and an office staff member to lead implementation in each practice. Practices will choose by month 4 SEEKonline or the Traditional paper and pencil approach. To ease introduction of the SEEK model, we will address logistical issues such as for which checkups parents will complete the SEEK PQ and documentation in the EHR. SEEK Parent Handouts will be customized with information on local resources and PCPs will complete the SEEK Primary Care Provider Questionnaire (PCPQ) prior to the SEEK training.

**Implementation Phase.** In month 5, practices in cohort 1 will be randomized to one of the two SEEK training strategies (MOC or IND), stratified by practice type (pediatric or family medicine). At the end of training in month 8, PCPs will evaluate it. After the training, PCPs will be asked to participate in 3 webinars

every 4 months to discuss implementation and clinical issues. By month 8, interested practices will have SEEKonline connected to their EHR, ensuring interoperability. In month 9, the SEEK intervention will begin in cohort 1. Practice leaders, PCPs, behavioral health professionals and office staff will be asked to complete the online SEEK Adoption Survey, regardless of full participation. Parents also will begin completing surveys. Purposive subsamples from each group will be selected for 30-minute phone qualitative interviews. The process for cohort 2 will begin in month 11 and the SEEK intervention will start in month 16. Procedures are detailed under Human Subjects for addressing concerns of possible child abuse or neglect.

**Sustainment Phase.** Participants will be assessed at 12, 21 and 33 months post baseline regarding their thinking, feeling, behavior and experiences (see Table 3) to help inform understanding of SEEK's implementation and sustainment. At months 41 and 48, the observation period will end for cohorts 1 and 2. Final surveys and phone interviews will assess participants' thoughts and plans about continued use of SEEK. Following the grant period, practices that wish to continue utilizing the implementation strategies will be guided through the process of establishing real-world, not-grant funded contracting.

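### The one-time training evaluation and the training-time PCPQ are scheduled before the live-data part of MOC training can take place

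*Combined protocol and SAP*

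**What the plan says.** The Training paragraph (section on the SEEK Model) describes MOC as the training videos plus putting SEEK into practice and running a Plan-Do-Study-Act (PDSA) cycle. That cycle "involves learning from data collected before and during" SEEK's implementation. Four "one-hour webinars over 4 months enable collaborative learning and mentoring". Table 1 lists "Engage in SEEK QI project – PDSA cycle" and the four webinars for MOC and marks both as not applicable to IND. IND consists of 2-3 hours of videos and a post-test. Both arms also receive three one-hour consultations over the following year.

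The Timeline puts these steps in months 1-8: "Recruit practices and randomly assign to SEEK training strategies; complete training". Procedures (Implementation Phase) randomises cohort 1 in month 5 and continues: "At the end of training in month 8, PCPs will evaluate it". It then says: "In month 9, the SEEK intervention will begin in cohort 1". For the second cohort the Timeline reads "Month 11-15: Repeat above process with cohort 2 of healthcare systems and practices", with SEEK starting in month 16.

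Table 3 marks the training evaluation once, in the Training column (cohort A by month 9, cohort B by month 10). It marks the PCPQ at baseline, in the Training column, and at follow-ups 1, 2 and 3. The Data Analysis Plan for Aim 1 compares the arms on the training evaluations and on PCPQ scales, among other outcomes. Its example model has one baseline and one follow-up. POST flags any measure taken after training, with no visit named.

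**The concern.** The live-data part of the PDSA cycle is one of the things that separates MOC from IND, and it needs SEEK to be running in the practice. On the printed dates, training is finished and rated before SEEK starts. By then an IND participant can have received everything that arm offers, while an MOC participant cannot.

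Two measures are exposed. The training evaluation has no later wave, so the randomised comparison of how clinicians rate their training would set a complete programme against an incomplete one. The training-time PCPQ satisfies the definition of POST as written. If it were chosen, the Competence and Comfort contrast under Aim 1 H1 would reflect MOC without the experience of using SEEK with one's own data. The sponsor's own rationale (response 5 in the Introduction to Proposal) credits implementation in practice and collaborative webinars with building self-efficacy, so the omitted part is one the sponsor expects to matter.

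**Working it through.** **Calendar check.** Inputs are the months in the Timeline, Procedures and Table 3.

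| | Cohort 1 (A) | Cohort 2 (B) |
|---|---|---|
| Training or process window | months 5-8 (8 - 5 + 1 = 4 months) | months 11-15 (15 - 11 + 1 = 5 months) |
| SEEK starts | month 9 | month 16 |
| Months of SEEK delivery inside the window | 0 | 0 |
| Training column of Table 3 | by month 9: 9 - 9 = 0 months after start | by month 10: 10 - 16 = -6 months |
| Follow-up 1 | 20 - 9 = 11 months after start | 27 - 16 = 11 months after start |
| Follow-up 3 | 41 - 9 = 32 months after start | 48 - 16 = 32 months after start |

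The four-month webinar series fits cohort 1's four-month window exactly, and data from before implementation can be gathered in it. The part of the PDSA cycle that uses data from during implementation cannot fall inside it. The same holds for cohort 2.

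The three webinars that Procedures schedules after training match in number the three consultations that Table 1 gives to both arms. They do not supply the MOC-only content.

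**The plan's own power figure.** Table 4 gives a detectable effect of 0.42 for PCP Comfort and Competence, with 137 per group, 80% power, a two-sided 0.05 test and a 1.5-fold inflation.

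- Effective n per group = 137 / 1.5 = 91.3.
- Detectable effect = (1.960 + 0.842) × √(2 / 91.3) = 0.415 by the normal formula, or 0.417 by the t distribution. The latter rounds to 0.42, so the figure is reproduced.

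**What attenuation would mean.** The documents give no share of the MOC effect that would be visible before live use, so the shares below are assumptions. With a full effect of 0.42 and standard error √(2 / 91.3) = 0.148, power ≈ Φ(share × 0.42 / 0.148 - 1.960):

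| Assumed share visible early | Effect | Power |
|---|---|---|
| 100% | 0.420 | 81% |
| 90% | 0.378 | 72% |
| 75% | 0.315 | 57% |
| 50% | 0.210 | 29% |

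These apply only if the training-time PCPQ is used as POST.

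**Related dates in Table 3.** Cohort B's Training date (by month 10) comes before that cohort's process starts in month 11 and before its month 15 baseline. Cohort A's month 8 baseline coincides with the end of training, although Procedures has the PCPQ completed before training. These need reconciling in the same pass.

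**The case against.** The strongest reply is that MOC support was meant to run on into delivery. The paragraph on facilitating implementation describes the interactive training as offering individual guidance when services start up, the Timeline has periodic webinars from month 5 to month 48, and no end date is given for the quality-improvement project. On that reading, the training that ends in month 8 is the videos, post-test and webinar series, and the project continues afterwards. This is plausible, and if right it means MOC can be delivered as defined. But the statements that training is completed by month 8 would then be wrong for MOC, and the single training evaluation would still precede part of the programme it rates.

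Several stronger readings are tempting, and the documents do not support them:

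- A reader might infer that the whole post-training comparison is compromised. It is not. The PCPQ is repeated at follow-ups 1-3, and the Aim 1a model is offered as an example that ties POST to no visit.
- A reader might infer that MOC is measured without everything that distinguishes it. The webinars are also MOC-only and fit before month 9; only the live-data part of the PDSA cycle does not.
- A reader might infer a definite bias towards no difference. An early measure follows four months of webinars in one arm and a few hours of video in the other, so it could also catch MOC's contrast at its largest. Attenuation is possible, not shown.
- A reader might infer a further conflict from cohort 2's short window. A four-month series fits in five months, so the only contradiction shown there is the same ordering.

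**Conclusion.** The contradiction stands on the documents' own dates: zero months of SEEK delivery fall inside the training window in either cohort, although MOC is defined to use data from delivery. The training evaluation is affected whichever reading of the MOC project is taken, because it is collected once, at the end of training. The training-time PCPQ is affected only if it serves as POST, and the size of any attenuation cannot be estimated from the documents.

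Follow-ups 1-3 are not affected, assuming the MOC cycle is finished within the 11 months between SEEK start and follow-up 1; the documents give no end date that would confirm this. No sample size or power figure is shown to be wrong.

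**What to change.** 1. Reconcile the Training paragraph and Table 1 with the Timeline and Procedures by stating when the MOC quality-improvement cycle ends relative to SEEK start in each cohort. Correct the related Table 3 dates at the same time.
2. In the Aim 1a model, name follow-up 1 (month 20 for cohort 1, month 27 for cohort 2) or a later wave as POST, and label the training-time PCPQ an interim measure. This also removes the choice among four post-baseline waves in the main randomised contrast.
3. Collect the training evaluation in both arms on the same date, after the MOC cycle is complete. Moving the form in the MOC arm alone would confound arm with timing and with experience of using SEEK.

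The cost is timeline wording, one named visit and a later date for one online form. The downside is slightly longer recall of training in the IND arm.
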